### 4.0 Procedures Involved

4.1 Study Design: This will be a 24-week, randomized, double-blind, placebo-controlled pilot and feasibility clinical trial of LDX plus lifestyle therapy versus matching placebo plus lifestyle therapy. We will enroll 44 children who have previously failed to lose weight with lifestyle therapy per parent report.

PROTOCOL TITLE: Lisdexamfetamine for the Treatment of Severe Obesity in Children Aged

6 to 12 Years

VERSION DATE: 19Sep2025

[figure not shown]

Figure 3. Clinical Trial Framework

The schedule of events shows the data that will be collected at each study visit. All participants will receive reimbursement for completing study visit assessments.

PROTOCOL TITLE: Lisdexamfetamine for the Treatment of Severe Obesity in Children Aged

6 to 12 Years

VERSION DATE: 19Sep2025

| SION DATE. 1936p2023                           |             |                                                 |                    |                    |                    |                    |                     |                     |                     |              |                     |                     |                     |                     |
|------------------------------------------------|-------------|-------------------------------------------------|--------------------|--------------------|--------------------|--------------------|---------------------|---------------------|---------------------|--------------|---------------------|---------------------|---------------------|---------------------|
|                                                | X Screening | Baseline/
Randomization
+21d  | Week 2 ± 3d | Week 4 + 3d | Week 6 + 3d | Week 8 ± 3d | Week 10 + 3d | Week 12 + 7d | Week 14 + 7d | Week 16 ± 7d | Week 18 + 7d | Week 20 + 7d | Week 22 + 7d | Week 24 + 7d |
| Informed Consent                               | X           |                                                 |                    |                    |                    |                    |                     |                     |                     |              |                     |                     |                     |                     |

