| Inclusion/Exclusion                | X           |                                                 |                    |                    |                    |                    |                     |                     |                     |              |                     |                     |                     |                     |
| Demographics                                   | X           |                                                 |                    |                    |                    |                    |                     |                     |                     |              |                     |                     |                     |                     |
| Medical history, including chemical dependency | X           |                                                 |                    |                    |                    |                    |                     |                     |                     |              |                     |                     |                     |                     |
| Height, weight, blood pressure and heart rate  | X           | X                                               |                    | X                  |                    | X                  |                     | X                   |                     | X            |                     | X                   |                     | X                   |
| Physical exam                                  | X           | Λ                                               |                    | Λ                  |                    | Λ                  |                     | Λ                   |                     | Λ            |                     | Λ                   |                     | Λ                   |
| Tanner stage                                   | X           |                                                 |                    |                    |                    |                    |                     |                     |                     |              |                     |                     |                     | X                   |

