#### 4.2 Study Procedures:

- Height, weight, blood pressure, heart rate and pubertal development. Height and weight will be measured by a calibrated, wall-mounted stadiometer and an electronic scale, respectively. Measurements will be obtained with participants in light clothing, without shoes. Two consecutive height and weight measurements will be obtained and averaged. If the first two values differ by more than 0.5 cm for height and/or 0.3 kg for weight, a third measurement will be obtained and the average of three measurements will be calculated. BMI will be calculated as the weight in kilograms divided by the height in meters, squared. Blood pressure will be obtained on the same arm using the same cuff size and equipment according to standardized procedures and the internal standard operating procedure. Tanner stage will be determined by trained personnel.
- Medical history and history of chemical dependency. Participants will be asked about their medical history at the screening visit and will be asked if they have a history of chemical dependency.
- Bone age. To estimate the maturity of the participant's skeleton, an x-ray of the left wrist will be taken.
- Resting energy expenditure. Resting energy expenditure will be measured by indirect calorimetry after participants have been fasting for ≥ 12 hours. Metabolic data will be collected using a ventilated hood. Participants will be instructed not to engage in intentional exercise or consume caffeine on the day prior to testing. Participants will be instructed to take their study medication the morning of their 24-week visit. Resting gas exchange measurements will be collected using a Parvo Medics TrueOne 2400 Metabolic Cart (Sandy,UT). After a 30-minute resting session, room air will be drawn through the hood at a rate of 25-40 L/min to match participant's respiration (dilution method). VO2 and VCO2 values will be collected over a 30-minute period in a semi-supine position to estimate resting metabolic rate. An estimate of metabolic rate will consist of an average of the 30-minute collection period minus the first 5-minutes and any movement and/or abnormal respiration. The metabolic cart will be calibrated for gas analyses and volume prior to each testing session.
- Blood analyses. Safety labs consisting of a basic metabolic panel and TSH at screening. Fasting blood (≥ 12 hours) will be collected for measurement of lipids (total-, LDL-, and HDL-cholesterol and triglycerides), glucose, insulin,

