# 12.0 Risks to Participants

#### 12.1 Foreseeable Risks:

Risks of blood sampling: There is a minimal risk of bruising, fainting and infection associated with blood draws.

Risks of exposure to ionizing radiation: The DXA scans and the bone age scans involve exposure to a very low dose of ionizing radiation. The average amount of radiation that the average person would receive from the bone age scan and DXA scans used in this study is less than 2% (3 mrem) of that received from natural sources of radiation by a Minnesota resident in one year (300 mrem).

Risks of Lisdexamfetamine: Adverse reactions occurring in ≥5% and at a rate at least twice that of placebo in children include anxiety, dry mouth, diarrhea, nausea, vomiting, upper abdominal pain, irritability, insomnia and dizziness. Rarely reported adverse events include hypertension and tachycardia. Additionally, suppression of linear growth is a known class effect, though final adult height is not impacted.

Although not recommended as a routine practice, baseline ECG will be obtained on all participants to screen for underlying arrhythmia. If SBP and/or DBP is ≥95th percentile or ≥130/80 (whichever is lower), blood pressure will be measured again on a separate visit within 2 weeks. If BP remains elevated on 3 separate visits, the participant will undergo a 24 hour ambulatory blood pressure monitor (ABPM) to confirm or rule out a diagnosis of hypertension.

If elevated BP emerges and is confirmed on 2 additional occasions during lisdexamfetamine dose escalation, further dose escalation will halt until the results of a 24 hour ABPM are available.

If hypertension is confirmed, lisdexamfetamine dose will be reduced until blood pressure normalizes.

- If SBP and/or DBP is ≥95th percentile+12 mmHg or ≥140/90 (whichever is lower) and the participant is symptomatic, lisdexamfetamine will be discontinued and the participant will be referred to emergent care.
- If heart rate is ≥140 bpm, an EKG will be obtained and the participant will be assessed for the need for emergent or non-emergent medical intervention, including the need to reduce or discontinue lisdexamfetamine dose.

*Risks of indirect calorimetry*: Potential risks include feeling claustrophobic from the mask/hood.

PROTOCOL TITLE: Lisdexamfetamine for the Treatment of Severe Obesity in Children Aged 6 to 12 Years

VERSION DATE: 19Sep2025

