**H2:** We hypothesize that at least 80% of participants will tolerate an LDX dose of ≥30 mg daily (recommended starting dose) for 24 weeks and that the LDX group compared to the placebo group will not demonstrate clinically significant increases in blood pressure or heart rate.

We will define feasibility to conduct the larger trial if, in this pilot study, >80% of participants randomized to LDX tolerate a dose of >30 mg daily, the recommended starting dose, for 24 weeks and there are no statistically significant differences between the LDX group and placebo group in incidence of developing stage 1 hypertension or tachycardia. Outcomes will be captured for all regardless of tolerability and will inform inclusions/exclusion criteria and dose escalation schedule for the subsequent trial. Safety outcomes will be monitored carefully and include instances of stage 1 hypertension (defined as SBP and/or DBP ≥95th percentile on 3 separate occasions) and confirmed by 24 hour ambulatory blood pressure monitor) and tachycardia (defined as heart rate ≥120 bpm at rest measured on 3 separate occasions). The Barkley Side Effect Rating Scale will also be measured at every 2 weeks during dose escalation and then every 4 weeks for the remainder of the study and will be used to help identify reasons for limited tolerability should this occur. Height velocity in cm/year will be determined by the difference in measured height between the baseline and 24-week assessments and will be used to calculate a height velocity SDS (z-score). Given the potential for LDX to disrupt sleep and the impact of sleep on obesity, participant sleep will be measured objectively using accelerometry with the ActiGraph (GT3X-BT) device, which has been shown to have acceptable reliability and validity in sleep-wake detection compared with laboratory-based polysomnography. Nighttime sleep efficiency, defined as the portion of time dedicated to sleep that is spent asleep, will be evaluated as the primary sleep endpoint of interest, with higher scores representing more efficient sleep. All indexes will be calculated using the ActiLife software. Participant mental health will be monitored by the Columbia-Suicide Severity Rating Scale (C-SSRS) and Children's Depressive Inventory-2 (CDI-2).

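### Height velocity uses only the baseline and week-24 heights; adding a slope analysis of all seven scheduled heights would be a cheap, modest gain in precision

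*Combined protocol and SAP*

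**What the plan says.** Section 14.0, under Aim 2, defines the measure from two visits: "Height velocity in cm/year will be determined by the difference in measured height between the baseline and 24-week assessments". The result "will be used to calculate a height velocity SDS (z-score").

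The schedule of events in Section 4.1 has a row for "Height, weight, blood pressure and heart rate", marked at screening, baseline and weeks 4, 8, 12, 16, 20 and 24. The visit lists in Section 7.3 agree. Seven heights therefore run from baseline to week 24 at four-week steps. Section 4.2 sets the measurement rule: "Two consecutive height and weight measurements will be obtained and averaged", and "If the first two values differ by more than 0.5 cm for height and/or 0.3 kg for weight, a third measurement will be obtained".

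On relevance, Section 12.1 states that "suppression of linear growth is a known class effect", and Section 2.1 says that the joint effect of drug and obesity on growth needs study. Height velocity appears neither in H2 nor in the feasibility criterion, which name tolerability, blood pressure or stage 1 hypertension, and heart rate or tachycardia. Section 14.0 calls the safety analyses mainly descriptive and sets no precision target for height velocity.

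**The concern.** A 24-week difference has to be multiplied by about 2.2 to become cm/year, and the measurement error in the two end heights is multiplied with it. The five heights in between are collected anyway and carry information about the same growth rate. With 22 children per arm, precision available at no cost in data collection is worth having on a measure tied to a stated class effect.

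Two practical points add to this. A child without a week-24 height has no observed two-point velocity. The week-24 visit also has a window of ±7 days, and the plan does not say whether elapsed time is nominal or actual. Seven days is 7/168 = 4.2% of the interval.

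**Working it through.** The plan gives no SD, power or precision figure for height velocity, so there is nothing of its own to reproduce. The check compares two estimators.

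**Inputs from the documents.** Heights at weeks 0, 4, 8, 12, 16, 20 and 24 (Section 4.1); 44 children randomised 1:1, so 22 per arm (Section 1.1).

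**Assumed inputs.** s is the SD of the error in one visit's height after the within-visit averaging in Section 4.2. The 0.5 cm tolerance there does not fix s. τ is the true between-child SD of velocity.

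**Step 1: error variance per child,** with linear growth and independent, equal-variance errors.
- Two-point velocity: 2s²/24² = 0.003472 s² per week².
- Least-squares slope: s²/Sxx, where Sxx = 16 × (9+4+1+0+1+4+9) = 448, giving 0.002232 s² per week².
- Ratio: 0.002232/0.003472 = 0.643, so variance is 35.7% lower. On the SD scale, √0.643 = 0.802, or 19.8% lower.

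**Step 2: annualise.** The factor is 52.18/24 = 2.174. At s = 0.3 cm the error SD is √2 × 0.3 × 2.174 = 0.92 cm/year for two points. For the slope it is √(576/448) × 0.3 × 2.174 = 0.74 cm/year.

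**Step 3: contrast between arms.** SE = √[2(τ² + error variance)/22]. True variation between children does not shrink, so the gain is diluted. With complete data at the scheduled times, the arm-by-time contrast from a model with random intercept and slope equals the difference in mean per-child slopes, so these figures apply to it.

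| s (cm) | τ (cm/year) | SE, two-point | SE, slope | Reduction |
|---|---|---|---|---|
| 0.1 | 2.0 | 0.610 | 0.608 | 0.4% |
| 0.2 | 1.0 | 0.354 | 0.336 | 5.0% |
| 0.3 | 1.0 | 0.410 | 0.375 | 8.6% |
| 0.5 | 1.0 | 0.553 | 0.479 | 13.5% |
| 0.5 | 0.5 | 0.487 | 0.401 | 17.7% |

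The first and last rows are the extremes over s = 0.1 to 0.5 cm and τ = 0.5 to 2 cm/year. In the middle row total variance falls from 1.85 to 1.55 (16%), and the half-width of the 95% CI from 0.80 to 0.74 cm/year.

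**Step 4: correlated errors.** With an assumed AR(1) correlation per four-week step, the variance ratio from step 1 becomes 0.80 at 0.2, 0.95 at 0.4 and 1.05 at 0.6. The gain shrinks and then reverses. A constant offset for a child cancels in both methods.

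**Step 5: non-linear growth.** If velocity halves after week 8, the two-point value is 0.667 of the starting velocity and the slope is 0.643. If the change comes at week 12, both are 0.750.

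**Step 6: a child seen through week 20 only.** Sxx for weeks 0 to 20 is 280. The planned two-point value has the equivalent of 24²/2 = 288. Such a child's slope still has nearly the planned error precision (288/280 = 1.03 times the variance).

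**The case against.** The strongest reply is that the plan is right as it stands. The difference over 24 weeks estimates mean velocity over that period without assuming linear growth. The planned dose rises over the first eight weeks, so a constant growth rate on drug cannot be taken for granted, and a straight-line slope then estimates a slightly different quantity. Each end height is already an average of two or three readings. This all stands, and it is why the two-point value should be kept.

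A reader might infer that a child who misses week 24 drops out of this outcome. The documents do not support that: Section 14.1 plans chained-equation imputation for missing follow-up data under all aims, with results also shown without it. What remains is narrower. The variables named for the imputation models do not include the intermediate heights, and the final visit after withdrawal in Section 11 does not list a height.

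A reader might also infer that the choice decides whether a growth signal can be detected, or that a key outcome is compromised. Neither follows. The measure is outside H2 and the feasibility criterion, the pilot is not sized on power, and the change in standard error is modest under most of the assumptions above.

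**Conclusion.** The point holds as a low-cost improvement. The plan forgoes a reduction of about 36% in measurement-error variance, or about 20% in error SD, if growth is roughly linear and visit errors are independent. That figure concerns measurement error only. For the comparison of arms the gain is about 9% of the standard error at s = 0.3 cm and τ = 1.0 cm/year, and 0.4% to 18% over the wider range. Both SDs are assumptions, and error correlation of around 0.4 or more per four-week step would remove nearly all of the gain. The firmer benefits are that heights already collected would be used for children without a week-24 value, and that actual dates and a between-arm estimate would be specified where the plan is silent.

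**What to change.** Keep the two-point velocity and its SDS as defined. Add to Section 14.0 a between-arm estimate from a linear mixed model on all heights from baseline to week 24. It should use actual visit dates, a random intercept and slope per child, and an arm-by-time contrast in cm/year with a 95% CI. Do not compute individual SDS values from the model's random-slope predictions: these are shrunk toward the mean and would compress the SDS.

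The cost is a few sentences in the SAP and no new data. The downside is the assumption of approximately linear growth, which is least secure during dose escalation. Setting the model estimate beside the two-point result checks it.

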# 15.0 Health Information and Privacy Compliance

| 15.1 | Select which of the following is applicable to your research: |
|------|---------------------------------------------------------------|
|      |                                                               |

☐ My research does not require access to individual health information and therefore assert HIPAA does not apply.

X I am requesting that all research participants sign a HIPCO approved HIPAA

PROTOCOL TITLE: Lisdexamfetamine for the Treatment of Severe Obesity in Children Aged 6 to 12 Years

| VERSION DATE: | 19Sep2025 |
|----------------------|-----------|
|----------------------|-----------|

15.2

15.3

|   | ATE, 100 an 2025                                                                                                                                                                                                                                                            |
|---|-----------------------------------------------------------------------------------------------------------------------------------------------------------------------------------------------------------------------------------------------------------------------------|
| I | ATE: 19Sep2025  Disclosure Authorization to participate in the research (either the standalone form or the combined consent and HIPAA Authorization).                                                                                                                       |
|   | ☐ I am requesting the IRB to approve a Waiver or an alteration of research participant authorization to participate in the research.                                                                                                                                        |
|   | Appropriate Use for Research:                                                                                                                                                                                                                                               |
|   | ☐ An external IRB (e.g. Advarra) is reviewing and we are requesting use of the authorization language embedded in the template consent form in lieu of the U of M stand-alone HIPAA Authorization. Note: External IRB must be serving as the privacy board for this option. |
|   | Identify the source of Private Health Information you will be using for your research (Check all that apply)                                                                                                                                                                |
|   | X I will use the Informatics Consulting Services (ICS) available through CTSI (also referred to as the University's Information Exchange (IE) or data shelter) to pull records for me                                                                                       |
|   | X I will collect information directly from research participants.                                                                                                                                                                                                           |
|   | □ I will use University services to access and retrieve records from the Bone
Marrow Transplant (BMPT) database, also known as the HSCT
(Hematopoietic Stem Cell Transplant) database.                                                                                |
|   | X I will pull records directly from EPIC.                                                                                                                                                                                                                                   |
|   | $\square$ I will retrieve record directly from axiUm / MiPACS                                                                                                                                                                                                               |
|   | $\square$ I will receive data from the Center for Medicare/Medicaid Services                                                                                                                                                                                                |
|   | $\square$ I will receive a limited data set from another institution                                                                                                                                                                                                        |
|   | □ Other. Describe:                                                                                                                                                                                                                                                          |
|   | Explain how you will ensure that only records of patients who have agreed to have their information used for research will be reviewed.                                                                                                                                     |
|   | We will work with Fairview Research Administration to pull a pool of individuals who have agreed, in their electronic medical record, to learn about potential research studies. The data will be placed in the data shelter so that recruitment                            |

research will not be approached.

letters and/or emails can be generated and sent to potential participants. Individuals who have indicated that they do not want to be contacted about

PROTOCOL TITLE: Lisdexamfetamine for the Treatment of Severe Obesity in Children Aged 6 to 12 Years

VERSION DATE: 19Sep2025

Practitioners within the Pediatric Weight Management Clinic may approach patients who they feel might qualify for the study and discuss the study with the patient. The patient may be provided with a flyer with the study name and a QR code to submit a request for additional information.

| QR code to                                                                                                                         | submit a reques                                                                                                                                                                                                                                                                                                                                                                                                                                                                                                                                                                                                                                                                                                                                                                                                                                                                                                                                                                                                                                                                                                                                                                                                                                                                                                                                                                                                                                                                                                                                                                                                                                                                                                                                                                                                                                                                                                                                                                                                                                                                                                                | at for additional information.                                                                                                                                                                                                                                                                                                                                                                                                                                                                                                                   |  |  |  |  |
|------------------------------------------------------------------------------------------------------------------------------------|--------------------------------------------------------------------------------------------------------------------------------------------------------------------------------------------------------------------------------------------------------------------------------------------------------------------------------------------------------------------------------------------------------------------------------------------------------------------------------------------------------------------------------------------------------------------------------------------------------------------------------------------------------------------------------------------------------------------------------------------------------------------------------------------------------------------------------------------------------------------------------------------------------------------------------------------------------------------------------------------------------------------------------------------------------------------------------------------------------------------------------------------------------------------------------------------------------------------------------------------------------------------------------------------------------------------------------------------------------------------------------------------------------------------------------------------------------------------------------------------------------------------------------------------------------------------------------------------------------------------------------------------------------------------------------------------------------------------------------------------------------------------------------------------------------------------------------------------------------------------------------------------------------------------------------------------------------------------------------------------------------------------------------------------------------------------------------------------------------------------------------|--------------------------------------------------------------------------------------------------------------------------------------------------------------------------------------------------------------------------------------------------------------------------------------------------------------------------------------------------------------------------------------------------------------------------------------------------------------------------------------------------------------------------------------------------|--|--|--|--|
| 15.4                                                                                                                               | Approximate                                                                                                                                                                                                                                                                                                                                                                                                                                                                                                                                                                                                                                                                                                                                                                                                                                                                                                                                                                                                                                                                                                                                                                                                                                                                                                                                                                                                                                                                                                                                                                                                                                                                                                                                                                                                                                                                                                                                                                                                                                                                                                                    | number of records required for review: >10,000                                                                                                                                                                                                                                                                                                                                                                                                                                                                                                   |  |  |  |  |
| Please describe how you will communicate with research participants during the course of this research. Check all applicable boxes |                                                                                                                                                                                                                                                                                                                                                                                                                                                                                                                                                                                                                                                                                                                                                                                                                                                                                                                                                                                                                                                                                                                                                                                                                                                                                                                                                                                                                                                                                                                                                                                                                                                                                                                                                                                                                                                                                                                                                                                                                                                                                                                                |                                                                                                                                                                                                                                                                                                                                                                                                                                                                                                                                                  |  |  |  |  |
| $\hfill\Box$ This research involves record review only. There will be no communication with research participants.                 |                                                                                                                                                                                                                                                                                                                                                                                                                                                                                                                                                                                                                                                                                                                                                                                                                                                                                                                                                                                                                                                                                                                                                                                                                                                                                                                                                                                                                                                                                                                                                                                                                                                                                                                                                                                                                                                                                                                                                                                                                                                                                                                                |                                                                                                                                                                                                                                                                                                                                                                                                                                                                                                                                                  |  |  |  |  |
